	at 95%, estimated from randomization date to the date of death,
	whatever the cause, using the Kaplan-Meier method.
	Secondary endpoints: The accordary efficacy endpoint include:
	The secondary efficacy endpoint include:
	- Progression-free survival (PFS), defined as the time (days) from
	date of randomization to date of first observed disease
	progression (investigator's radiological or clinical assessment) or
	death due to any cause, if death occurs before progression is
	documented. Patients without tumor progression or death at the
	time of analysis will be censored at their last date of tumor
	assessment.
	- Time to Deterioration is defined as the time between the date of
	randomization and the first time the patient has a WHO ≥ 2 during
	treatment.
	- Disease control rate (DCR), defined as the rate of patients,
	whose best response was not progressive disease (i.e., CR, PR or
	SD), to all randomized patients in the treatment group
	- Objective response rate (OOR), defined as the rate of patients
	with CR or PR, to all randomized patients in the treatment group.
	Patients prematurely discontinuing without an assessment will be
	considered non-responders for the analysis.
	- Safety will be evaluated using the NCI-CTCAE version 5.0 scale;
	at each visit for the duration of the treatment.
	-Quality of life will be evaluated, using the EORTC QLQ-C30
	questionnaire.
	The expected benefit is an overall survival improvement of this
	treatment in patients with metastatic colorectal cancer who have
	received all standard treatments except TAS-102 and
	Regorafenib.

RISK AND BENEFITS	Toxicity and tolerance will be clinically and biologically assessed and rated on the NCIC CTCAE V5.0 scale at each visit. The expected benefit is an improvement in the overall survival of this treatment in patients with metastatic colorectal cancer who have received all standard treatments except TAS-102 and regorafenib. The risks of the study are continuously assessed by the MHI's pharmacovigilance department. This risk-benefit will be discussed in periodic safety reports. These reports will include all regulatory aspects and will be submitted to the competent authorities.
ELIGIBILITY CRITERIA	
	Signed informed consent obtained before any study specific procedures
	2. Male or female ≥ 18 years of age
	Histological documentation of adenocarcinoma of the colon or rectum
	Patients with metastatic colorectal cancer

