2.2.2 Secondary endpoints

The secondary efficacy endpoints include:

- Progression-free survival (PFS), defined as the time (days) from date of randomization to date of first observed disease progression (investigator's radiological or clinical assessment) or death due to any cause, if death occurs before progression is documented. Patients without tumor progression or death at the time of analysis will be censored at their last date of tumor assessment.
- Time to Deterioration is defined as the time between the date of randomization and the first time the patient has a WHO \geq 2 during treatment.
- Disease control rate (DCR), defined as the rate of patients, whose best response was not progressive disease (i.e., CR, PR or SD), to all randomized patients in the treatment group-Objective response rate (OOR), defined as the rate of patients with CR or PR, to all randomized patients in the treatment group. Patients prematurely discontinuing without an assessment will be considered non-responders for the analysis.

- Safety will be evaluated by clinical and biological means and scored on the NCI-CTCAE version 5.0 scale, performed at each visit (every 2 weeks).
- -Quality of life will be evaluated, based on the EORTC QLQ-C30 questionnaire (appendix 2).

[figure not shown]
3. Experimental plan

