5.1 Tabulated overview

Tabulated overview NEXT-REGIRI	Screening					Regorafenib (1 cycle = 4 weeks (1 cycle = every 15 days and 1 cycle = every 4 weeks)						Evaluation (Every 8 weeks)	End of treatment	Safety Follow-up ^c .	Follow-up	End of study
Baseline Documentation	As early as second- line	~ 28 days	Within 28 days	Within 14 days	Within 7 days	CX D1ª	C1, C2 D8	CX D1 ^a	C1, C2 D8	Cx D15	C1, C2 D22	~8 weeks	~14 days	~30 days	Follow-up: every other month	
Molecular testing informed consent	Х															
Clinical trial informed consent			Х													
Complete medical history			Х													
Inclusion/Exclusion Criteria			Х													
Physical examination					Χ	Χ		Χ		Χ			Χ			
β-HCG blood test					Χ	Χ		Χ								
Status of Ras, Raf and MSI have to be known		Χ														
Laboratory Studies																
12-lead ECG					Χ	X ¹		X ¹				Х	X ⁴			
Complete blood count					Χ	Χ		Χ		Χ			X ⁴			
Coagulation					Х	Х		Х		Х			X ⁴			
Electrolyte panel					Х	Х		Х		Х			X ⁴			
Chemistry panel					Χ	Х		Х		Х			X ⁴			

							,	Treatment							
Tabulated overview NEXT-REGIRI		Screening				Regorafenib (1 cycle = 4 weeks		e = every 15 d	EGIRI lays and 1 cy eeks)	cle = every 4	Every 8 weeks	End of treatment b,e	SafetyFollo w-up ^{c-d}	Follow- up	End of study
Liver function test panel				Х	X ²		Х	Χ	Χ	Х		X ⁴			
Thyroid function				Χ	Χ		Χ					X ⁴			
Tumor markers				Χ	X ³		X ³				Χ	X ⁴	X ⁵		
Urinary analysis				Χ	Χ		Χ		Χ			X ⁴			
Imaging assessments															
Radiologic Tumor assessment d		Х									Χ	X ⁶	X ⁵		
Other Clinical Assessments															
ECOG				Х	Х		Х		Χ			X ⁴			
Body weight, BSA, height, and vital signs				Х	Х		Х	X ⁷	Χ			X ⁴			
Concomitant medications			Х		Х		Χ		Χ			Χ	Х		
Adverse events				Χ	Χ		Χ	Χ	Х	Χ		Χ	Χ		
Drug dispensing					X8		X8								
Drug accountability					X8		X8		Χ			Х			
Post-study survival status														Х	
Anti-cancer medications														Х	
Patient's diary					X ⁹		X ⁹		Χ						
Patient Reported Outcomes															
Quality of life questionnaires					X ¹⁰		X ¹⁰				Χ				
Phone call : adverse events, blood pressure					Х	Х				X					
Ancillary study															
Immunohistochemistry ^e															X

- a: Cycle 1 Day 1 : the laboratory evaluations are not required at day 1 of cycle 1 if those were completed within 7 days
- b: Within 14 days (+/- 7 day) after study treatment has stopped
- c: Within 30 days (+/- 7 day) after study treatment has stopped

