5.3 Treatment period

REGIRI or Regorafenib:

After all screening assessments have been completed and the patient's eligibility has been confirmed and documented, the patient will be randomized.

The following assessments should be performed on the first day and day 15 of each cycle (REGIRI) or cycle (Regorafenib) except C1D1 prior to receiving study treatment (+/- 3 days):

- Physical examination with weight, body surface area (if the patient's body weight changes by more than 10 % then BSA will be recalculated for Regorafenib and it will be recalculated for any change of weight for Irinotecan) and vital signs (heart rate, blood pressure)
- ECOG performance status :
- Adverse events documentation (including Start/Stop dates, seriousness, CTC notation and grading, relationship to study drug, outcome and action taken) using CTCAE V5.0
- Concomitant medications (including start/stop dates, dose, indication)
- 12-lead ECG. It will be performed every other cycle (8 weeks if there's no postponed treatment) for both arms
- The following laboratory evaluations are not required at Day 1 of Cycle 1 if these
 were completed within 7 days of starting study drug treatment. Otherwise, these
 laboratory evaluations are required on Day 1 and 15 of each cycle:
 - → CBC with differential should be performed: RBC, hemoglobin, hematocrit, platelet count and WBC. WBC must include differential neutrophil, lymphocyte, monocyte, basophil and eosinophil counts
 - → Coagulation panel: Prothrombin time (PT) or the International Ratio of PT (PT-INR) and Partial Thromboplastin Time (PTT)
 - → Electrolyte panel: sodium, potassium, chloride, calcium
 - → Chemistry panel : albumin, lipase, phosphate, glucose, serum creatinine, clearance calculated according CKD-EPI (appendix 7)
 - → Hepatic panel: Aspartate Amino-Transferase (AST), Alanine Amino-Transferase (ALT), bilirubin (total and direct), GGT, alkaline phosphatase, Lactic Dehydrogenase (LDH)

- → Thyroid function test (TSH, free T3, free T4, on day 1 of each cycle for both arms)
- Tumor markers CEA (Carcino-Embryogenic Antigen), CA 19-9 (carbohydrate Antigen 19-9) every cycle for both treatments
- A β-HCG dosage for women of childbearing potential. Post-menopausal women with no menses for at least 1 year or surgically sterilized women will not be required to undergo a pregnancy test (on day 1 of each cycle for both arms).
- Urine analysis by urinary dipstick. If results of protein ≥ 3+, then quantification

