 of proteinuria on a 24-hour urine collection must be done.
- EORTC QLQ-C30 (appendix 2) questionnaires will be completed by the patient on Day 1 of Cycle 1 (baseline) then on the first day of every other cycle (every 8 weeks)
- Drug dispensing
- Drug accountability (pharmacy). To have complete control over the distribution and use of the study drug, the drug accountability must be performed on Day 1 for arm A (REGIRI) and B (Regorafenib) of each cycle

Provide patient's diary on C1D1. It will allow to patient to write down his oral intakes and blood pressure values

The blood pressure must be monitored weekly for the first six weeks of study treatment. The blood pressure will be recorded by the patient and entered onto his treatment diary. In the latter case, the patient should be instructed to contact the physician in the event of systolic \geq 150 mm Hg and / or diastolic \geq 100 mm Hg. The physician should confirm the reading before recording it into the e-CRF. Blood pressure measurements will be performed in patients sitting for 5 minutes prior to the evaluation. The patient should be instructed to take their blood pressure in the morning and repeat two more times for accuracy.

The following assessments should be performed on day 8 of cycle 1 and 2:

REGIRI (arm A)

- Vital signs (Heart rate and blood pressure)
- these laboratory evaluations are required: Aspartate Amino-Transferase (AST), Alanine Amino-Transferase (ALT), bilirubin (total and direct)

Stivarga® (Regorafenib) (arm B):

• Phone call by a treatment nurse for knowing if there are any adverse events and blood pressure value (current state of the art)

The following assessments should be performed on day 15 of cycle 1 and 2:

REGIRI (arm A)

- Physical examination with weight and vital signs (heart rate, blood pressure)
- ECOG performance status
- Concomitant medications (including start/stop dates, dose, indication)
- Adverse events documentation (including Start/Stop dates, seriousness, CTC notation and grading, relationship to study drug, outcome and action taken) using CTCAE V5.0
- A CBC with differential should be performed: RBC, hemoglobin, hematocrit, platelet count and WBC. WBC must include differential neutrophil, lymphocyte, monocyte, basophil and eosinophil counts
- Coagulation panel: Prothrombin time (PT) or the International Ratio of PT (PT-INR) and Partial Thromboplastin Time (PTT)
- Electrolyte panel: sodium, potassium, chloride, calcium

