- Chemistry panel: albumin, lipase, phosphate, glucose, serum creatinine, clearance calculated according CKD-EPI (appendix 7)
- Hepatic panel: Aspartate Amino-Transferase (AST), Alanine Amino-Transferase (ALT), bilirubin (total and direct), GGT, alkaline phosphatase, Lactic Dehydrogenase (LDH)
- Urine analysis by urinary dipstick. If results of protein ≥ 3+, then quantification of proteinuria on a 24-hour urine collection must be done.
- Drug accountability (pharmacy)
 Verify patient's diary. It will allow to patient to write down his oral intakes and blood pressure values

The following assessments should be performed on day 15 of cycle 1 and 2:

Stivarga® (Regorafenib - arm B):

• these laboratory evaluations are required: Aspartate Amino-Transferase (AST), Alanine Amino-Transferase (ALT), bilirubin (total and direct)

The following assessments should be performed on day 22 of cycle 1 and 2:

REGIRI (arm A):

- Phone call by a treatment nurse for knowing if there are any adverse events and blood pressure value (current state of the art)
- These laboratory evaluations are required: Aspartate Amino-Transferase (AST),
 Alanine Amino-Transferase (ALT), bilirubin (total and direct)

The following assessments should be performed at each evaluation i.e (every 8 weeks):

REGIRI or Regorafenib:

 Tumor markers CEA (Carcino-Embryogenic Antigen), CA 19.9 (Carbohydrate Antigen 19-9)

 Radiological tumor assessment using the RECIST criteria, version 1.1 (see Appendix 5) must be performed. (CT scan of the abdomen, pelvis and chest or hepatic MRI and CT scan of the pelvis and chest without injection)

A PET scan is not acceptable for radiological evaluation. Throughout the study, the identical lesions to those identified and measured at baseline must be evaluated using the same technique, and preferably by the same radiologist. Copies of all CT scans performed for tumor assessment in non-progressive enrolled patients will be stored on CDs at the site

 EORTC QLQ-C30 (appendix 2) questionnaires will be completed by the patient at each evaluation i.e 8 weeks

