9.3 Statistical methods

A Statistical Analysis Plan (SAP) will be written before the database is locked. Populations are defined in section 9.2.

All statistical analyses will be performed on ITT population.

Safety analysis will be performed on safety population

Sensitivity analysis will be performed on Modified Intent To Treat (ITT) population for primary endpoint.

Descriptive analyses (in each arm) will be performed using median and range for continuous parameters, frequency and percentage for categorical variables.

Baseline characteristics of randomized patients in each arm will be compared by Kruskal-Wallis tests or Wilcoxon for continuous variables, or chi 2 or Fisher exact test for categorical variables

The primary efficacy endpoint of OS will be compared using a two-sided stratified log-rank test. The analysis will be stratified by RAS. Kaplan-Meier (KM) estimates for OS and KM survival curves will also be presented for each group. The KM estimates at time points such as 6 months and 12 months, together with corresponding 95% confidence intervals as well as the differences of these estimates will be calculated between the REGIRI and Regorafenib arms.

With regard to the secondary efficacy endpoint PFS, the 2 treatment groups will be compared using a log-rank test stratified by RAS. Hazard ratios and 95% CI will be provided. KM estimates and KM curves will also be presented for each treatment arm. The KM estimates at time points such as 3 months and 6 months, together with corresponding 95%

Protocole NEXT-REGIRI -Version 6.0 du 09/11/2023

confidence intervals as well as the differences of these estimates between the REGIRI arm and the Regorafenib arm will also be calculated.

Objective response rate as well as DCR will be compared between treatment groups using the Cochran-Mantel-Haenszel test. Estimates and 95% confidence intervals will be computed for each treatment arm. The differences in ORR and DCR between the REGIRI and regorafenib arms and the corresponding 95% confidence intervals will also be calculated.

Summary statistics will be displayed for all best response categories: CR, PR and SD.

Descriptive summary tables will be presented for all safety parameters by each treatment group. All AEs, as well as drug-related AEs and SAEs will be summarized by NCI-CTCAE version 5 (appendix 9) categories and worst grade.

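### The plan contradicts itself on how often adverse events are asked about in each arm; if the visit table is followed, regorafenib patients miss the stated two-week interval and AE ascertainment is unequal.

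*Combined protocol and SAP*

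**What the plan says.** **Section 2.2.2** defines the safety endpoint as "scored on the NCI-CTCAE version 5.0 scale, performed at each visit (every 2 weeks"). It names no arm. The synopsis says only "at each visit for the duration of the treatment", with no interval.

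**Section 5.3, joint list**, under a heading that names both treatments: "The following assessments should be performed on the first day and day 15 of each cycle (REGIRI) or cycle (Regorafenib) except C1D1". One item in that list is "Adverse events documentation (including Start/Stop dates, seriousness, CTC notation and grading, relationship to study drug, outcome and action taken) using CTCAE V5.0".

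**Section 5.1, visit table.** The adverse-event row is marked for regorafenib on D1 only. For REGIRI it is marked on D1 and D15 of every cycle and on D8 and D22 of cycles 1-2. A separate row, "Phone call : adverse events, blood pressure", adds D8 for regorafenib and falls on D22 for REGIRI in cycles 1-2.

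**Section 5.3, arm-specific lists for cycles 1-2.**
- D8: REGIRI has vital signs and liver tests with no AE item; regorafenib has a "Phone call by a treatment nurse for knowing if there are any adverse events and blood pressure value".
- D15: REGIRI has full AE documentation. For regorafenib the list reads "these laboratory evaluations are required: Aspartate Amino-Transferase (AST), Alanine Amino-Transferase (ALT), bilirubin (total and direct") and nothing else.
- D22: REGIRI has an AE phone call; regorafenib has no entry.

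**Section 9.3** plans descriptive tables by arm: "All AEs, as well as drug-related AEs and SAEs will be summarized by NCI-CTCAE version 5" categories and worst grade. It states no between-arm test of AEs. It also says that the SAP will be written before the database is locked.

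**The concern.** Toxicity is a secondary objective (section 2.1.2), the trial is open (3.1), and the AE tables set the two arms side by side. When one arm is asked about symptoms more often than the other, short-lived and low-grade events are more likely to be picked up in that arm even if the true rates are equal. In the control arm there is a specific exposed window. Regorafenib is taken on D1-D21, and under the table the last scheduled AE question of cycles 1-2 is on D8. A reaction that arises on D9-D21 is next asked about on D1 of the following cycle, after the week off drug. The patient diary (5.3) covers oral intakes and blood pressure, not symptoms. Part of an apparent toxicity excess for REGIRI could then come from the contact schedule, and the toxicity of the control treatment could be understated.

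**Working it through.** **1. The plan's own figure.** One assessment every 2 weeks is 28/14 = 2 per cycle in each arm. The joint list in 5.3, read as covering both arms, gives D1 and D15, which is also 2. These two places agree.

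**2. AE contacts per 28-day cycle, by source** (AE documentation or a call that asks about AEs).

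| Source | REGIRI, C1-C2 | Regorafenib, C1-C2 | REGIRI, C3 on | Regorafenib, C3 on |
|---|---|---|---|---|
| 5.1 table | D1, D8, D15, D22 = 4 | D1, D8 = 2 | D1, D15 = 2 | D1 = 1 |
| 5.3, D15 of joint list read as REGIRI only (narrow) | D1, D15, D22 = 3 | D1, D8 = 2 | 2 | 1 |
| 5.3, D15 of joint list read as both arms (broad) | D1, D15, D22 = 3 | D1, D8, D15 = 3 | 2 | 2 |

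Regorafenib/REGIRI over 6 cycles:
- Table: (2×2 + 4×1)/(2×4 + 4×2) = 8/16 = 0.50.
- Narrow: (2×2 + 4×1)/(2×3 + 4×2) = 8/14 = 0.57 (over cycles 1-2 alone, 4/6 = 0.67).
- Broad: (2×3 + 4×2)/(2×3 + 4×2) = 14/14 = 1.0.

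The table and the text also disagree on REGIRI D8: the table has an AE mark, the list has no AE item.

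**3. Longest gap for regorafenib under the table.** Cycles 1-2: D8 to D29 = 21 days. From cycle 3: D1 to D29 = 28 days. Both exceed 14 days.

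**4. Possible size in cycles 1-2, with equal true rates.** The following are assumptions and are not in the documents: onset uniform over days 1-56; exponential duration with mean 3 or 7 days; an event is recorded if still present at the next contact, otherwise with probability 0.5^(days since resolution / half-life). Contact days up to C3D1:
- REGIRI, table: 1, 8, 15, 22, 29, 36, 43, 50, 57.
- REGIRI, day lists: 1, 15, 22, 29, 43, 50, 57.
- Regorafenib, table or narrow reading: 1, 8, 29, 36, 57.
- Regorafenib with D15: 1, 8, 15, 29, 36, 43, 57.

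| Mean duration | Recall half-life | Recorded under table, REGIRI vs regorafenib | Ratio, table | Ratio, narrow lists |
|---|---|---|---|---|
| 3 days | 7 days | 86% vs 62% | 1.39 | 1.25 |
| 3 days | 14 days | 92% vs 76% | 1.22 | 1.14 |
| 3 days | 28 days | 96% vs 86% | 1.11 | 1.08 |
| 7 days | 7 days | 92% vs 72% | 1.28 | 1.18 |
| 7 days | 14 days | 96% vs 83% | 1.16 | 1.11 |
| 7 days | 28 days | 98% vs 90% | 1.08 | 1.06 |

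Ratios are taken before rounding. On the broad reading the ratio is 1.00 throughout. With full recall it is 1.00 under any schedule. If D15 is added for regorafenib but REGIRI keeps the table's D8 and D22, it is 1.02 to 1.12.

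**5. Outer bound from cycle 3, with no recall at all.** For a fixed duration d and gap g, the capture probability is min(1, d/g), with g = 14 for REGIRI and 28 for regorafenib under the table. For d = 7: 0.50 vs 0.25. For d = 14: 1.00 vs 0.50. For d = 21: 1.00 vs 0.75. For d = 28: equal. The ratio runs from 2.0 down to 1.0.

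**The case against.** A reader might infer that the plan asks control patients about AEs half as often and that the comparison is therefore biased against REGIRI. The documents do not support that as a settled fact.

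- **Half holds for the table only.** The day lists give 3 vs 2 in cycles 1-2 on the narrow reading, and on D8 they ask the control arm, not REGIRI, about AEs. This stands.
- **The joint list can be read as equal.** Read broadly, it gives equal contacts and agrees with 2.2.2. This stands as a possible reading, but it does not settle the matter: if that list governed arm B, a separate D15 list with liver tests alone would be redundant.
- **The table is weak evidence of intent.** Its regorafenib block, as it reads, has no D15 column, and the arm B D15 liver tests appear only through a footnote to the D1 cell. The missing AE mark may be a layout omission. That is fair, but a site working from the table still sees no D15 AE assessment for arm B.
- **Recording is not tied to contact days.** Section 10.1.2 requires every AE to be recorded with onset and end dates, and SAEs are notified without delay (10.2.4.1). This limits the effect and largely protects SAEs. It sets no days for questioning, so minor resolved events still depend on recall.
- **The tables are descriptive and use worst grade.** Counting patients rather than events dilutes the effect. If events of one type per patient are Poisson with mean 2 (an assumption), the largest table ratio becomes (1 − e^(−2×0.862))/(1 − e^(−2×0.619)) = 0.822/0.710 = 1.16. The effect is smaller but not removed.

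**Conclusion.** The inconsistency is established: 2.2.2 and the joint list in 5.3 conflict with the table in 5.1 and with the arm-specific lists on whether regorafenib patients have an AE assessment on D15, and the table and the text conflict on D8 for REGIRI. If the table is followed, the control arm does not meet the plan's own two-week interval.

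Bias in the AE comparison is possible, not shown. Its likely direction under the table or the narrow reading is more recorded events in REGIRI, mainly short-lived, low-grade ones; SAEs are much less affected. In cycles 1-2 the illustrated ratio is about 1.1 to 1.4 under the table and 1.06 to 1.25 under the narrow day lists. These figures rest wholly on the assumed durations and recall half-lives. The ratio is 1.0 with full recall or if D1 and D15 apply to both arms.

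**What to change.** 1. Reconcile 5.1 and the arm-specific lists in 5.3 with 2.2.2 and the joint list, so that AE documentation is marked on D1 and D15 of every cycle in both arms. For regorafenib, the existing D15 liver-test contact can carry this in cycles 1-2; a phone call is enough later.
2. Resolve the D8 and D22 AE items so that the table and the text agree and the two arms match in cycles 1-2.
3. In the SAP, report the number of AE contacts per arm, and flag the all-grade AE tables as subject to unequal ascertainment for patients treated under the table.

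The cost is a correction of the table and lists, short nurse calls of the kind already planned, and a few sentences in the SAP. Arm B has slightly more contact, and its recorded AE rates may rise. Protocol version 6.0 is dated November 2023, about 50 months into a 64-month inclusion period that began in September 2019. A change now could therefore mix two levels of ascertainment within arm B, which is a further reason to report the contact counts.
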